4.1 Weighted Least Squares (WLS)

A linear regression of the meter results (MeterBG) against the YSI reference method results (LabBG) via weighted least squares (WLS) will be performed, with weights:

$$w = \frac{1}{YSI^2}$$

used to account for the proportional variance nature of blood glucose measurements (Draper and Smith, 1998)².

4.2 Studentized Residuals and Outlier Identification

Studentized residuals from the regression will be computed, i.e.,

² Draper, N. R., Smith, H., (1998) Applied Regression Analysis, 3rd Ed., John Wiley and Sons

$$e_i = y_i - \hat{y}_i$$

$$\varepsilon_i = \frac{e_i}{s_e \sqrt{1 - h_{ii}}}$$

That is, a studentized residual, ε , is the residual, e , divided by the standard error, $s_e \sqrt{1 - h_{ii}}$, of the residual. The variables h_{ii} are the diagonal elements of the “hat” matrix:

$$\mathbf{H} = \mathbf{X}[\mathbf{X}'\mathbf{W}^{-1}\mathbf{X}]^{-1}\mathbf{X}'\mathbf{W}^{-1}$$

The matrix \mathbf{W} is a diagonal matrix with the regression weights, $w = \frac{1}{YSI^2}$ on the diagonal.

A meter result will be considered an “outlier” if its corresponding studentized residual is outside the interval $(\Phi^{-1}(0.005), \Phi^{-1}(0.995)) \approx (-2.576, +2.576)$, corresponding to a 99% interval for a standard normal variate. The function $\Phi^{-1}(p)$ is the inverse cumulative distribution function of a standard normal random variable; that is, the function is a z-score.

Confidence bands (99%) for the regression (individual) predictions will be computed. Scatter plots of MeterBG vs. LabBG will be constructed, with the regression line, the confidence bands, and the line of identity ($Y = X$) will all be plotted.

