4.3 Radar Plots

Radar plots will be made. Two plots (one with units of mg/dL and one with units of mmol/L) will be constructed using only PWD data (ISO), and will include ISO 15197:2013 bifurcation of criteria (difference for $YSI < 100$ mg/dL, relative difference when $YSI \geq 100$ mg/dL). Another plot will be constructed for all evaluable data (FDA) in mg/dL.

5. Error Grid Analyses

Parkes consensus error grids will be constructed for combined strip lots, and combined sites as described in Tables 6.1 and 6.2. There is no criterion for percentage of values within the error grid zones.

6. Data Analysis Schemes

Table 6.1 -Data Analysis Scheme (per ISO15197:2013)

Blood Type	Data Comparison	Regression Tables	Bland Altman Plots	Accuracy	Error Grid	Error Interval tables (5,10,15, 20, >20%)
Capillary	Subject vs. YSI	x*	x***	x*	x*	x*
	Staff vs YSI	x*	x***	x*	x*	x*
Venous	Results vs. YSI	x*	x***	x*	x*	x*

* Combined sites

*** Plots with different symbols denoting whether observations are outliers

Table 6.2 -Data Analysis Scheme (per draft FDA OTC Guidance 2018)

Blood Type	Data Comparison	Regression Tables	Scatter Plots	Accuracy	Error Grid	Error Interval tables (5%,7%,10%,15%,20%)
Capillary	Subject vs. YSI	x*	x***	x*	x*	x*
	Staff vs YSI	x*	x***	x*	x*	x*

* Combined sites

*** Plots with different symbols denoting whether observations are outliers

Note – Samples outside +/- 20% will be identified and listed (per draft FDA 2018).

7. Subject Questionnaires

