Level mmol/L	Variable	N	Mean	Std Dev	Min	Max	Median
LT 5.55	D (mg/dL)	74	0.12	0.25	-0.69	0.84	0.15
GE 5.55	RD (%)	297	3.17	4.945	-28.09	25.36	3.23

[figure not shown]
Section 4 – Regression Plot

Table 4.1 Regression Statistics

Variable	Term	Estimate	Std Error	LCL	UCL	Adj. R ²	RMSE	d.f.e.
Sub.Cap.	Intercept	1.253	0.9989	-0.712	3.218	0.9827	0.0481	322
	YSICAP	1.024	0.0076	1.009	1.039			322
AST	Intercept	0.834	1.3671	-1.856	3.524	0.9672	0.0663	323
	YSICAP	1.008	0.0103	0.988	1.029			323
Staff Test	Intercept	-0.776	0.8393	-2.427	0.875	0.9882	0.0405	322
	YSICAP	1.044	0.0063	1.032	1.057			322
Venous	Intercept	3.035	1.6399	-0.192	6.261	0.9506	0.0819	316
	YSIVEN	0.988	0.0127	0.963	1.013			316
Estimate = Least Squares Value								
Std Error = Standard Error of Estimate								
LCL = Lower Confidence Limit								
UCL = Upper Confidence Limit								
Adj. R ² = Adjusted R-squared								
RMSE = Root Mean Square Error								
d.f.e. = Degrees of Freedom for Error								

Figure 4.1. Regression Plot

Section 4 – Modified Bland-Altman Plot

Figure 4.2. Modified Bland-Altman Plot

Note: D-SCP-O represents differences (D) for points identified as outliers; D-SCP-N are non-outlier points. LL-diff and UL-diff are the ISO 15197:2013, section 8 limits on accuracy.

[figure not shown]
Section 5 – Consensus (Parkes) Error Grid

Figure 5.1. Parkes Error Grid

GCA-PRO-2014-002-01
Karajishi Contour(R) - Staff Capillary

Parkes Error Grid Analysis

Zone	A	B	C	D	E
Freq	326 out of 326	0 out of 326			
%Freq	100.0%	0.0%	0.0%	0.0%	0.0%

Section 7 – Subject Questionnaires

Table 7.1. Ease of Use Statements

Statement No.	Ease of Use
S1	I find it easy to do a fingerstick blood test with this meter.
S2	The meter display is easy to see and read.
S3	It was easy to understand my test results.
S4	I like the overall meter design.
S5	I find the meter easy to use.
S6	The instructions (User Guide and Quick Reference Guide) were easy to understand.
S7	The instructions clearly explain how to run a test.
S8	The instructions clearly explain what to do if an error message is displayed by the meter.

Table 7.2. Ease of Use Results

Note: columns labeled % ≥ Neutral and Crit. % will not appear in the table for the FDA report.

	Strongly Disagree	Disagree	Neutral	Agree	Strongly Agree	Total No. Answered	% ≥ Neutral	Crit. %
S1	1	3	19	98	251	372	98.92%	87.63%
S2	1	0	1	76	294	372	99.73%	87.63%
S3	1	0	11	64	296	372	99.73%	87.63%
S4	2	2	39	125	204	372	98.92%	87.63%
S5	1	2	11	93	265	372	99.19%	87.63%

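### The outlier formula in SAP 4.2 leaves out the regression weight and does not define s_e, so ±2.576 is not a 99% limit under the SAP's own variance model

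*SAP*

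**What the plan says.** SAP 4.1 regresses the meter result on the YSI result "via weighted least squares (WLS) will be performed, with weights" of 1/YSI², "used to account for the proportional variance nature of blood glucose measurements".

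SAP 4.2 (Studentized Residuals and Outlier Identification) sets e_i = y_i − ŷ_i and defines the studentized residual as e_i "divided by the standard error, $s_e \sqrt{1 - h_{ii}}$, of the residual". It gives no formula, unit or subscript for s_e. The leverages h_ii come from H = X[X'W⁻¹X]⁻¹X'W⁻¹, where W "is a diagonal matrix with the regression weights" 1/YSI². A result is an outlier if this ratio falls outside (−2.576, +2.576), "corresponding to a 99% interval for a standard normal variate".

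The footnotes to Tables 6.1 and 6.2 give the use of the flag: "Plots with different symbols denoting whether observations are outliers". It applies to the Bland-Altman plots in the ISO scheme and the scatter plots in the FDA scheme. The note to mock Figure 4.2 shows the same use: "D-SCP-O represents differences (D) for points identified as outliers".

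**The concern.** The weighting in 4.1 means that the residual standard deviation is proportional to YSI. A studentized residual must then be scaled observation by observation. The printed one divides every raw residual by the same s_e, apart from the small leverage term, so its spread changes with glucose and no single cut-off can cover 99% at all levels.

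A programmer following the text must also guess s_e. The one regression error shown is the column in mock Table 4.1 labelled "RMSE = Root Mean Square Error" (0.0481 for subject capillary results), which is on a relative scale and is not identified as s_e.

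What is at stake is how the plots in two study reports are read. A low-glucose result with a large relative error could carry the ordinary symbol, while an unremarkable high-glucose result is marked as an outlier.

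**Working it through.** **The SAP's own figure.** Φ⁻¹(0.995) = 2.5758, and Φ(2.576) − Φ(−2.576) = 0.9900. The cut-off is right for a standard normal variable. Using t with 322 degrees of freedom instead would give 2.591, which is a negligible difference.

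**The right scale.** Under 4.1, Var(y_i) = σ²·YSI_i², so the standard deviation of e_i is σ·YSI_i·√(1 − h_ii), with h_ii from H = X(X'WX)⁻¹X'W and W = diag(1/YSI²). The statistic that is approximately standard normal is therefore √w_i·e_i / (s_w·√(1 − h_ii)), where s_w² = Σw_i·e_i²/(n − 2). The printed ratio lacks √w_i.

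**Inputs, used as assumptions.** The mock tables are facsimiles.
- Relative error 0.0481 (mock Table 4.1, subject capillary).
- Capillary YSI for all subjects: mean 147.49, SD 69.119. For diabetes only: mean 154.39, SD 70.405 (mock Table 9.1).
- n = 350 for all subjects (SAP 1.2) and n = 324 for diabetes only (mock Table 11.1).
- A lognormal glucose distribution, which the documents do not state.

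**Reading A: s_e is the unweighted value in mg/dL.** It is about 0.0481 × √(147.49² + 69.119²) = 0.0481 × 162.9 = 7.8 mg/dL. The flag limit is 2.576 × 7.83 ≈ 20.2 mg/dL at every glucose level, ignoring leverage:

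| LabBG (mg/dL) | 20.2 mg/dL as % of value |
|---|---|
| 50 | 40% |
| 70 | 29% |
| 250 | 8% |
| 300 | 6.7% |

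If the fitted line is close to identity, this limit equals the ISO ±15% limit at 20.2/0.15 ≈ 135 mg/dL. Below that level a result can fail the ISO limit and not be flagged. Above it, a result can be flagged while inside the limit.

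**Reading B: s_e is the weighted value, 0.0481.** The limit is 2.576 × 0.0481 = 0.12 mg/dL, because a mg/dL residual is divided by a relative error.

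**Simulation.** 2,000 data sets per scenario: MeterBG = LabBG × (1 + RMSE·z) with z standard normal, weighted fit with w = 1/LabBG². Percentage flagged:

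| Formula and scenario | <100 | 100–250 | >250 mg/dL |
|---|---|---|---|
| Weighted formula, all subjects | 0.98 | 0.98 | 0.97 |
| As printed, reading A, all subjects | 0.0 | 1.5 | 18.1 |
| As printed, reading A, diabetes only | 0.0 | 1.4 | 16.3 |

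Above 250 mg/dL, reading A gives 16.3% with the staff-test error of 0.0405 and 17.1% with the venous values (mean 150.91, SD 70.353, n = 318, error 0.0819). Reading B flags 98.3% of all results. A second simulation of the diabetes-only case used the mock intercept and slope and glucose truncated to the mock range. It gave 0% below 100, 15.5 to 16.0% above 250, and about 98% under reading B.

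**Single planted errors, all subjects, reading A.**

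| Planted error | Flagged as printed | Flagged by weighted formula |
|---|---|---|
| +25% at 70 mg/dL | 0.7% | 100% |
| +30% at 70 mg/dL | 66% | 100% |
| +35% at 70 mg/dL | 99% | 100% |
| +35% at 50 mg/dL | 0.5% | 100% |
| +50% at 50 mg/dL | 99.8% | 100% |
| +8% at 300 mg/dL | 98% | 0% |

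**The hat matrix.** W is defined as the weights, yet H uses W⁻¹, so leverage is computed as if the weights were YSI². Correcting H alone changes the reading A rates only from 0.0/1.5/18.1% to 0.0/1.5/17.5%. Weighting the residual but leaving H inverted gives 0.95/0.98/1.12%. This slip is real but numerically small.

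**The case against.** The best defence is that the intent is clear. The residuals come from the weighted fit, and the words describe division by the residual's standard error, which under 4.1 would include YSI. Mock Table 4.1 supports this. In a fit weighted by 1/YSI², the spread of 1/YSI can be recovered as RMSE/(SE of intercept × √(n − 1)), with n equal to the error degrees of freedom plus 2:
- Subject: 0.0481/(0.9989 × √323) = 0.00268.
- AST: 0.0663/(1.3671 × √324) = 0.00269.
- Staff: 0.0405/(0.8393 × √323) = 0.00268.

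Three rows with different errors imply the same spread, so that table appears to come from a properly weighted fit. Software may apply the weight by default, and an analyst would notice a plot with 98% of points flagged. This makes literal execution less likely. It does not repair the text: e_i is explicitly the raw difference, and s_e has no definition. If the software does something else, the SAP does not describe the analysis that was run.

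The inputs are also approximate. For all subjects the lognormal puts 12.5% of results below 80 mg/dL, against 22/375 = 5.9% in mock Table 9.1, although its share above 250 mg/dL fits (8.0% against 31/375 = 8.3%). The exact rates should not be leaned on. The direction does not depend on them, because a constant mg/dL limit applied to proportional error must under-flag low and over-flag high.

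Finally, the consequence is small. ISO limits are drawn on the Bland-Altman plots, error intervals are tabulated, and FDA results beyond ±20% are listed. That stands, and it limits the severity.

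**Conclusion.** The concern holds: the formula is wrong as written. Under the SAP's proportional-variance model the printed statistic is not standard normal, and ±2.576 does not give a 99% limit under either reading of s_e. With an unweighted s_e, about 0% of results are flagged below 100 mg/dL and about 16 to 18% above 250 mg/dL. With the weighted value, about 98% of all results are flagged. The intended rate is 1% throughout, and the weighted formula delivers it. The percentages rest on mock-table values and an assumed lognormal glucose distribution, so they indicate size only.

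Severity is minor. The flag changes plot symbols in the ISO and FDA analyses. It does not enter any acceptance criterion, and outlier status is not among the reasons for non-evaluability in SAP Section 11.

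**What to change.** In SAP 4.2:
- Define the studentized residual as √w_i·(y_i − ŷ_i) / (s_e·√(1 − h_ii)), with w_i = 1/YSI_i².
- State that s_e is the weighted root mean square error, s_e² = Σw_i·(y_i − ŷ_i)²/(n − 2).
- Write H = X(X'WX)⁻¹X'W with W = diag(1/YSI²). Alternatively, keep W⁻¹ and define W as the variance matrix diag(YSI²).

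The ±2.576 limit can stay. The cost is two formula corrections and one definition, with no effect on data collection or on any pass/fail rule.

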4.2 Modified Bland-Altman Plots

A Modified Bland-Altman Plot, with D plotted against LabBG (no limits on the range), will be constructed for subject-generated fingerstick, staff-generated fingerstick, and venous results. The limits for accuracy of individual results, per ISO:15197:2013, will also be plotted on the graphs.

4.3 Radar Plots

Radar plots will be made. Two plots (one with units of mg/dL and one with units of mmol/L) will be constructed using only PWD data (ISO), and will include ISO 15197:2013 bifurcation of criteria (difference for $YSI < 100$ mg/dL, relative difference when $YSI \geq 100$ mg/dL). Another plot will be constructed for all evaluable data (FDA) in mg/dL.

5. Error Grid Analyses

Parkes consensus error grids will be constructed for combined strip lots, and combined sites as described in Tables 6.1 and 6.2. There is no criterion for percentage of values within the error grid zones.

6. Data Analysis Schemes

Table 6.1 -Data Analysis Scheme (per ISO15197:2013)

Blood Type	Data Comparison	Regression Tables	Bland Altman Plots	Accuracy	Error Grid	Error Interval tables (5,10,15, 20, >20%)
Capillary	Subject vs. YSI	x*	x***	x*	x*	x*
	Staff vs YSI	x*	x***	x*	x*	x*
Venous	Results vs. YSI	x*	x***	x*	x*	x*

* Combined sites

*** Plots with different symbols denoting whether observations are outliers

Table 6.2 -Data Analysis Scheme (per draft FDA OTC Guidance 2018)

Blood Type	Data Comparison	Regression Tables	Scatter Plots	Accuracy	Error Grid	Error Interval tables (5%,7%,10%,15%,20%)
Capillary	Subject vs. YSI	x*	x***	x*	x*	x*
	Staff vs YSI	x*	x***	x*	x*	x*

* Combined sites

*** Plots with different symbols denoting whether observations are outliers

Note – Samples outside +/- 20% will be identified and listed (per draft FDA 2018).

7. Subject Questionnaires

7.1 Questionnaire 1 – Ease of Use

Subject questionnaire 1 will consist in part of questions/statements for which a numerical score or rating (1=strongly disagree, 2=disagree, 3=neutral, 4=agree, 5=strongly agree) will be provided by the subjects and entered by the study staff. For these numerically-scored questions, frequency distributions will be tabulated. For PWD subjects only (ISO 15197:2013 requirements), hypothesis tests for selected statements will be performed. The hypotheses are:

$$H_0: \Pr\{\text{response} \geq 3\} < 90\% \text{ versus the alternative:}$$

$$H_a: \Pr\{\text{response} \geq 3\} \geq 90\%$$

The critical number of responses greater than or equal to 3, X_c , is a function of the actual sample size, and will be chosen such that $0.95 = \sup \Pr\{X \geq X_c | 100p\% = 90\%\}$. For example, if $n = 315$, then $X_c = 276$, so that $\Pr\{X \geq X_c | 100p\% = 90\% \} \approx 0.9299 \leq 0.95$. That is, 276 is the number of responses ≥ 3 which yields the largest value of $\Pr\{X \geq X_c | 100p\% = 90\% \} \leq 0.95$ for $n = 315$.

7.2 Questionnaire 2, Diabetes Management

Frequencies of responses will be tabulated for statements/questions in the Diabetes Management Questionnaire.

8. Demographic, Diabetes History, Medications and Disease State Data

Descriptive statistics for subject Demographic, Diabetes History, Medications and Disease State data will be computed as appropriate. Histograms will be constructed where appropriate. A percentage of subjects < 65 years of age will be calculated.

9. Other Tables

9.1 Hematocrit Analysis

Hematocrit will be measured in singlet for each subject. For ISO 15197 analyses, subjects with a hematocrit determination that is out of range (outside the range 0-70%) cannot be used for blood glucose measurement comparisons.

The mean, median, minimum, maximum, and standard deviation, will be computed for hematocrit determinations.

9.2 Temperature and Humidity

Mean, median, standard deviation, minimum and maximum room temperature and humidity will be computed.

9.3 Glucose Distribution

The distribution of YSI glucose and a histogram (combined sites) for both capillary and venous blood will be provided. The mean, median, minimum, maximum, and standard deviation, will be computed for glucose distributions, by site and for both sites combined.

In addition, the number of capillary samples with concentrations <80 and > 250 mg/dL will be reported.

10. Data Listing

A listing of the data (excel sheet) is needed for the clinical study report. The listing should include: subject and staff fingerstick meter results, venous meter results, AST results, capillary and venous YSI results, subject ID, hematocrit.

11. Data Evaluability

Blood glucose data will be considered not evaluable for the following reasons:

- Subjects with either no hematocrit result or a hematocrit result outside of meter specifications (0-70%) (for FDA accuracy analyses, there is no requirement to have a hematocrit value; this requirement only pertains to ISO analyses).
- BG readings from **subject** meter tests that the subject feels were incorrectly completed. (If the subject states that the test s/he performed was completed incorrectly, and repeats the test, then the new BG reading will be used as the subject test.) Tests of each type (e.g., subject fingerstick) made be performed up to 3 times, i.e., repeated up to 2 times if the tester feels that the test was performed improperly.

- Failure to separate the plasma from the red cells (for YSI analysis) within 15 minutes of obtaining the corresponding evaluation meter result.
- Discrepant YSI replicate results will be excluded[†]. The comparator value for the subject will be the average of the non-outlier replicates. Should only a single replicate value be obtained for a given subject, it will be used as the comparator value.
- Subject plasma samples that do not have in-range serum controls tested after subject plasma test will be considered non evaluable.

Note: If supplemental or unplanned analyses are requested they will be presented in a supplemental report.

[†] Glucose values of the YSI replicates should be **within ± 4 mg/dL when average of replicates < 100 or $\pm 4\%$ of each other when average of replicates ≥ 100** ; if not, an additional assay should be run.

12. Laboratory Instrument Quality Control

Runs using serum control material at multiple levels will be executed daily for each laboratory glucose comparator instrument used in the study. The run means will be compared to lower and upper limits for each level. If the minimum and maximum value of individual measurements are within lower and upper limits, the run means do not need to be compared to those limits also.

A regression line will be fit using the instrument results regressed against target values as set by Ascensia Diabetes Care analytical laboratory. For levels with target values below 75 mg/dL, the within-run and between standard deviation (SD) will be computed; for levels with targets great than or equal to 75 mg/dL, the coefficient of variation (CV) will be computed, using the average over all runs.

Scatterplots of control result against targets, together with regression lines, for each instrument will be constructed. The Differences from target will be plotted against the target values for each instrument.

13. Meter Control Solution Results

Each meter unit used in the study will have control solution tests performed. The acceptable range of control solution results is specific to each meter, and the limits are provided by R&D or Quality Assurance. The control solution results must fall within prescribed limits in order for a meter to be used in the study. There are up to 3 attempts allowed to obtain a within-limit result for each meter.

Mock Tables and Graphs

Mock tables and graphs are intended to illustrate the general nature of such tables and graphs that are to be included in the study report. As such, they are facsimiles; actual tables and graphs may vary from the mock versions. For example, studies may have more than one site. The actual tables indicating results are computed by site would have results for each site included in the study.

Section 3 – Proportions: Applies to Sections 3.1-3.3, 3.5, 3.7

Table 3.1. Proportion $-15 \text{ mg/dL} \leq D \leq +15 \text{ mg/dL}$ (LabBG < 100 mg/dL) or $-15\% \leq RD \leq +15\%$ (LabBG $\geq 100 \text{ mg/dL}$)

Level	Count	Percent	Lower CI	Upper CI	1-Alpha
In	317	97.84%	95.61%	98.95%	0.95
Out	7	2.16%	1.05%	4.39%	0.95
Total	324				

Section 3 – Descriptive Statistics for D, RD

[figure not shown]
Table 3.2. Descriptive Statistics for D and RD

Level mg/dL	Variable	N	Mean	Std Dev	Min	Max	Median
LT 100	D (mg/dL)	74	2.19	4.470	-12.40	15.20	2.75
GE 100	RD (%)	297	3.17	4.945	-28.09	25.36	3.23
Level mmol/L	Variable	N	Mean	Std Dev	Min	Max	Median
LT 5.55	D (mg/dL)	74	0.12	0.25	-0.69	0.84	0.15
GE 5.55	RD (%)	297	3.17	4.945	-28.09	25.36	3.23

[figure not shown]
Section 4 – Regression Plot

Table 4.1 Regression Statistics

Variable	Term	Estimate	Std Error	LCL	UCL	Adj. R ²	RMSE	d.f.e.
Sub.Cap.	Intercept	1.253	0.9989	-0.712	3.218	0.9827	0.0481	322
	YSICAP	1.024	0.0076	1.009	1.039			322
AST	Intercept	0.834	1.3671	-1.856	3.524	0.9672	0.0663	323
	YSICAP	1.008	0.0103	0.988	1.029			323
Staff Test	Intercept	-0.776	0.8393	-2.427	0.875	0.9882	0.0405	322
	YSICAP	1.044	0.0063	1.032	1.057			322
Venous	Intercept	3.035	1.6399	-0.192	6.261	0.9506	0.0819	316
	YSIVEN	0.988	0.0127	0.963	1.013			316
Estimate = Least Squares Value								
Std Error = Standard Error of Estimate								
LCL = Lower Confidence Limit								
UCL = Upper Confidence Limit								
Adj. R ² = Adjusted R-squared								
RMSE = Root Mean Square Error								
d.f.e. = Degrees of Freedom for Error								

Figure 4.1. Regression Plot

Section 4 – Modified Bland-Altman Plot

Figure 4.2. Modified Bland-Altman Plot

Note: D-SCP-O represents differences (D) for points identified as outliers; D-SCP-N are non-outlier points. LL-diff and UL-diff are the ISO 15197:2013, section 8 limits on accuracy.

[figure not shown]
Section 5 – Consensus (Parkes) Error Grid

Figure 5.1. Parkes Error Grid

GCA-PRO-2014-002-01
Karajishi Contour(R) - Staff Capillary

Parkes Error Grid Analysis

Zone	A	B	C	D	E
Freq	326 out of 326	0 out of 326			
%Freq	100.0%	0.0%	0.0%	0.0%	0.0%

Section 7 – Subject Questionnaires

Table 7.1. Ease of Use Statements

Statement No.	Ease of Use
S1	I find it easy to do a fingerstick blood test with this meter.
S2	The meter display is easy to see and read.
S3	It was easy to understand my test results.
S4	I like the overall meter design.
S5	I find the meter easy to use.
S6	The instructions (User Guide and Quick Reference Guide) were easy to understand.
S7	The instructions clearly explain how to run a test.
S8	The instructions clearly explain what to do if an error message is displayed by the meter.

Table 7.2. Ease of Use Results

Note: columns labeled % ≥ Neutral and Crit. % will not appear in the table for the FDA report.

	Strongly Disagree	Disagree	Neutral	Agree	Strongly Agree	Total No. Answered	% ≥ Neutral	Crit. %
S1	1	3	19	98	251	372	98.92%	87.63%
S2	1	0	1	76	294	372	99.73%	87.63%
S3	1	0	11	64	296	372	99.73%	87.63%
S4	2	2	39	125	204	372	98.92%	87.63%
S5	1	2	11	93	265	372	99.19%	87.63%
S6	2	2	31	105	232	372	98.92%	87.63%
S7	1	3	10	92	266	372	98.92%	87.63%
S8	1	0	17	98	256	372	99.73%	87.63%

Table 7.3. Diabetes Management Statements

Statement No.	Diabetes Mgt. Survey (PWDs Only)	
	Accuracy is important to help with:	
S1	1a)	My ability to talk with my Health Care Professional
S2	1b)	My satisfaction with my self-monitoring of diabetes.
S3	1c)	My ability to manage my diabetes.
S4	1d)	Preventing low blood sugars.
S5	1e)	Understanding how food or exercise affects low blood sugars.
S6	1f)	Using my results to gain better control of my diabetes.
S7	1g)	Achieving greater peace of mind.
S8	2. I prefer the meter that I just used to my regular meter	
	I use my current meter because:	
S9	3a)	My care provider gave it to me
S10	3b)	My insurance company covers the strips
S11	3c)	I think it is the most accurate meter

Table 7.4. Diabetes Management Results

Statement	SCORE						Total*
	0	1	2	3	4	5	
Question 1	3	0	0	12	54	263	329
Question 2	2	0	1	4	64	261	330
Question 3	1	0	2	6	53	270	331
Question 4	9	0	1	9	63	250	323
Question 5	2	0	1	8	58	263	330
Question 6	0	0	2	1	48	281	332
Question 7	2	1	2	10	67	250	330
Question 8	16	12	13	95	75	121	316
Question 9	40	22	21	21	67	161	292
Question 10	26	28	16	18	55	189	306
Question 11	24	16	33	135	76	48	308

*Total number of subjects who responded

Section 8 all of these tables below are needed for ALL and only PWD

Table 8.1. Ethnicity

Ethnicity	Count	Percent
Hispanic or Latino	47	12.63%
Not Hispanic or Latino	320	86.02%
Not Reported	5	1.34%
Total	372	100.00%

Table 8.2. Race

Race	Count	Percent
White	305	81.99%
Black	32	8.60%
Asian	23	6.18%
Native American	7	1.88%
Hawaiian/Pacific Islander	4	1.08%
Not Reported	7	1.88%

Table 8.3. Languages Spoken

Language Spoken	Count	Percent
English	363	97.58%
Spanish	10	2.69%
BUNGABA	1	0.27%
HINDI, PUNJABI	1	0.27%
KANNADA	1	0.27%
TAGALOG	2	0.54%
URDU	2	0.54%
VIETNAMESE	1	0.27%

Table 8.4. Education

Education	Count	Percent
Bachelors degree or more	110	29.57%
High school graduate or equivalent	66	17.74%
Less than high school	7	1.88%
Not reported	2	0.54%
Some college or Associate degree	187	50.27%
Total	372	100.00%

Table 8.5. Occupation

Occupation	Count	Percent
Administrative	109	29.30%
Manufacturing	43	11.56%
Professional	113	30.38%
Sales/Services	122	32.80%
Student	74	19.89%
Retired	96	25.81%
Health Care Field	53	14.25%
Work at home	51	13.71%
Other	42	11.29%
Not reported	2	0.54%

Table 8.6. Gender

Gender	Count	Percent
Female	201	54.03%
Male	171	45.97%
Total	372	100.00%

Table 8.7. Age Statistics

N	Mean	SD	Median	Min	Max	# < 65	% < 65
376	52.1	15.60	55	18	81	295	78.46%

Table 8.8. Diabetes Type

Type	Count	Percent
Do not have diabetes	43	11.56%
Don't know (Type 1 or Type 2)	3	0.81%
Type 1	121	32.53%
Type 2	205	55.11%
Total	372	100.00%

Table 8.9. Diabetes History (PWD Subjects Only)

Variable	Level	Count	Percent
Time	1 to 3 months	6	1.82%
Since	4 to 6 months	1	0.30%
Diagnosis	7 to 12 months	3	0.91%
	13 months to 2 years	22	6.69%
	3 to 5 years	25	7.60%
	6 to 10 years	58	17.63%
	More than 10 years	214	65.05%
	Total	329	100.00%
Testing	1 time per day	54	16.41%
Frequency	2 times per day	63	19.15%
	3 times per day	49	14.89%
	4 times per day	35	10.64%
	I don't test my blood glucose	11	3.34%
	Less than 1 time per day	39	11.85%
	More than 4 times per day	78	23.71%
	Total	329	100.00%
Recommended	1 time per day	57	17.33%
Testing	2 times per day	55	16.72%
Frequency	3 times per day	61	18.54%
	4 times per day	52	15.81%
	Less than 1 time per day	10	3.04%
	More than 4 times per day	81	24.62%
	My HCP does not recommend BG testing	13	3.95%
	Total	329	100.00%
Insulin	Insulin pump	75	35.21%
Use	One or two injections per day	57	26.76%
Frequency	Three or more injections per day	81	38.03%
	Total	213	100.00%

Table 8.9. Diabetes History Continued (PWD Subjects Only)

Variable	Level	Count	Percent
HbA1c	6.0 % or lower	23	6.99%
	6.1 to 6.5 %	37	11.25%
	6.6 to 7.0 %	48	14.59%
	7.1 to 7.5 %	63	19.15%
	7.6 to 8.0 %	32	9.73%
	8.1 to 8.5 %	25	7.60%
	8.6 to 9.0 %	8	2.43%
	9.1 to 9.5 %	17	5.17%
	9.6 to 10.0 %	7	2.13%
	10.1 to 10.5 %	2	0.61%
	Greater than 10.5 %	14	4.26%
	I don't know	52	15.81%
	I have never gotten an A1C test	1	0.30%
	Total	329	100.00%
Type of HCP	Diabetologist	1	0.30%
	Endocrinologist	149	45.29%
	General/ Family practitioner	159	48.33%
	Internist	12	3.65%
	Other	8	2.43%
	Total	329	100.00%
Other HCP	ARNP	1	12.50%
	COMMUNITY CLINIC	1	12.50%
	D.O	1	12.50%
	INTERNAL MEDICINE	1	12.50%
	NURSE PRACTITIONER	2	25.00%
	P.A.	1	12.50%
	RN	1	12.50%
	Total	8	100.00%
Use	I do not know what DMS is	12	3.65%
Data Mgt.	No	259	78.72%
Software	No (do NOT use at home)	29	8.82%
	Yes	29	8.82%
	Total	329	100.00%
DM Software	Daily	2	6.90%
Frequency	Less than monthly	4	13.79%
of Use	Monthly	6	20.69%
	Only in preparation for Doctor's appointment	14	48.28%
	Weekly	3	10.35%
	Total	29	100.00%

Table 8.9. Diabetes History Continued (PWD Subjects Only)

Adjust Therapy based on BG Results?	No	123	37.39%
	Yes	206	62.61%
	Total	329	100.00%
Manage Diabetes with Insulin?	No	116	35.26%
	Yes	213	64.74%
	Total	329	100.00%

Table 8.10. Subjects Taking Pre-Defined List of Medications

Subject take any Drugs Listed?	Count	Percent
No	17	4.57%
Yes	355	95.43%
Total	372	100.00%

Table 8.11. Numbers and Percents of Subjects Taking Pre-Defined Medications

Abbreviation	Drug Name	Count	Percent
AMARYL	Amaryl / Glimepiride	7	1.88%
ASPIRIN	Aspirin	163	43.82%
COFFEE	Coffee / Caffeine	291	78.23%
EPHEDRIN	Ephedrine/ (Sudafed)	19	5.11%
GLUCOPHA	Glucophage / Metformin	159	42.74%
GLUCOTRO	Glucotrol / Glipizide	19	5.11%
MICRONAS	Micronase /Glyburide	7	1.88%
MOTRIN	Motrin/Ibuprofen	139	37.37%
PIOGLITA	Pioglitazone / Actos	4	1.08%
TETRACYC	Tetracycline	1	0.27%
TYLENOL	Tylenol / Acetaminophen	98	26.34%
VITAMINC	Vitamin C / Ascorbic Acid	93	25.00%
None	None	17	4.57%

Table 8.12. No. PWD Subjects with Pre-Defined Conditions

Condition:	No. PWD w/Condition	No. PWD	% PWD
Have any of following?	209	329	63.53%
Parkinson's	0	329	0.00%
Liver Disease	2	329	0.61%
Kidney Disease	14	329	4.26%
Hyperlipidemia	146	329	44.38%
Gout	16	329	4.86%
Hypertension	154	329	46.81%
Cardiac Disease	19	329	5.78%

Table 8.13. No. Non-PWD Subjects with Pre-Defined Conditions

Condition:	No. Non-PWD w/Condition	No. Non-PWD	% Non-PWD
Have any of following?	8	43	18.60%
Parkinson's	0	43	0.00%
Liver Disease	1	43	2.33%
Kidney Disease	0	43	0.00%
Hyperlipidemia	6	43	13.95%
Gout	0	43	0.00%
Hypertension	2	43	4.65%
Cardiac Disease	0	43	0.00%

Table 8.14. No. All Types of Subjects with Pre-Defined Conditions

Condition:	No. ANY w/Condition	No. Total	% Total
Have any of following?	217	372	58.33%
Parkinson's	0	372	0.00%
Liver Disease	3	372	0.81%
Kidney Disease	14	372	3.76%
Hyperlipidemia	152	372	40.86%
Gout	16	372	4.30%
Hypertension	156	372	41.94%
Cardiac Disease	19	372	5.11%

Section 9 – Other Tables – 9.1 and 9.3

Table 9.1. LabBG and HCT Descriptive Statistics

Variable	Population	Site	N	Mean	SD	Median	Min	Max	< 80	> 250
YSI CAP	PWD	1	163	152.80	65.214	139.50	44.95	455.50	11	14
YSI CAP	PWD	2	169	155.92	75.237	135.50	32.25	458.00	11	17
YSI CAP	PWD	Both	332	154.39	70.405	136.00	32.25	458.00	22	31
YSI CAP	ALL	1	184	146.23	64.330	126.75	44.95	455.50	11	14
YSI CAP	ALL	2	191	148.71	73.586	127.50	32.25	458.00	11	17
YSI CAP	ALL	Both	375	147.49	69.119	127.50	32.25	458.00	22	31
Hematocrit	PWD	1	163	43.09	4.036	43	34	59		
Hematocrit	PWD	2	169	43.44	3.767	44	33	52		
Hematocrit	PWD	Both	332	43.27	3.899	43	33	59		
Hematocrit	ALL	1	184	43.02	3.939	43	34	59		
Hematocrit	ALL	2	191	43.41	3.742	43	33	52		
Hematocrit	ALL	Both	375	43.22	3.840	43	33	59		
YSI VEN	PWD	1	162	149.18	65.075	136.50	47.30	455.00	15	12
YSI VEN	PWD	2	168	152.58	75.251	131.25	30.25	461.00	16	16
YSI VEN	PWD	Both	330	150.91	70.353	133.50	30.25	461.00	31	28

Note: HCT = hematocrit; YSI = capillary YSI LabBG; YSI-VEN = venous YSI LabBG

Section 9 – Temperature (Temp) and Relative Humidity (RH)

Table 9.2. Temperature and Relative Humidity

Site	Variable	N	Mean	SD	Median	Min	Max
1	Temperature (°F)	28	70.42	0.581	70.4	68.5	71.8
2	Temperature (°F)	44	72.08	0.965	72.3	70.0	74.7
1	Relative Humidity (%)	28	36.89	5.370	39.0	24.0	44.0
2	Relative Humidity (%)	44	37.34	4.467	37.0	27.0	47.0
Both	Temperature (°F)	72	71.43	1.164	71.5	68.5	74.7
Both	Relative Humidity (%)	72	37.17	4.806	38.0	24.0	47.0

Section 11 – Evaluability

Table 11.1. Numbers of Non-Evaluables

RESULT TYPE	Total No. Subjects	Non-eval	Missing Meter BG	No HCT	Usable N
SUBJECT RESULT	372	1	5	1	365
STUDY STAFF RESULT	372	1	1	1	369
Non-PWD-SUB	43	0	2	0	41
Non-PWD-STAFF	43	0	0	0	43
Total PWDs	329				
PWDs used for ISO-SUB CAP					324
PWDs used for ISO-STAFF CAP					326
VENOUS	329	0	10	1	318
Note: 3006 had missing venous BG as well as missing HCT					

Section 12 – Laboratory Instrument Quality Control

Table 12.1. Accuracy Statistics

Site	YSINUM	LEVEL	Target	N	D = YSI - Target (mg/dL)				
					Mean(D)	Std Dev(D)	Median(D)	Min(D)	Max(D)
1	10	2	50.0	38	-0.44	0.606	-0.40	-1.60	0.70
1	10	3	98.5	38	0.05	1.023	0.35	-1.90	1.50
1	10	4	197.3	38	-1.35	1.355	-1.30	-3.30	1.70
1	10	5	394.5	38	-1.87	3.560	-2.50	-8.50	4.50
1	11	2	50.0	38	-0.73	0.812	-0.70	-2.40	1.60
1	11	3	98.5	38	-0.50	1.400	-0.20	-3.40	1.50
1	11	4	197.3	38	-2.09	2.055	-1.80	-5.30	1.70
1	11	5	394.5	38	-3.79	3.631	-3.50	-15.50	2.50
2	48	2	50.0	34	-1.24	0.595	-1.30	-2.20	0.00
2	48	3	98.5	34	-1.52	1.402	-1.45	-4.30	1.00
2	48	4	197.3	34	-3.56	2.300	-3.80	-7.30	0.70
2	48	5	394.5	34	-3.82	3.169	-4.00	-9.50	4.50
2	98	2	50.0	34	-1.30	0.535	-1.20	-2.30	-0.20
2	98	3	98.5	34	-1.42	1.431	-1.35	-4.30	1.00
2	98	4	197.3	34	-4.01	1.915	-4.30	-8.30	-0.30
2	98	5	394.5	34	-3.94	3.067	-4.00	-10.50	1.50

Site	YSINUM	LEVEL	Target	N	RD = 100(YSI - Target)/Target (%)				
					Mean(RD)	Std Dev(RD)	Median(RD)	Min(RD)	Max(RD)
1	10	2	50.0	38	-0.88	1.212	-0.80	-3.20	1.40
1	10	3	98.5	38	0.05	1.039	0.36	-1.93	1.52
1	10	4	197.3	38	-0.69	0.687	-0.66	-1.67	0.86
1	10	5	394.5	38	-0.47	0.902	-0.63	-2.15	1.14
1	11	2	50.0	38	-1.47	1.624	-1.40	-4.80	3.20
1	11	3	98.5	38	-0.50	1.421	-0.20	-3.45	1.52
1	11	4	197.3	38	-1.06	1.042	-0.91	-2.69	0.86
1	11	5	394.5	38	-0.96	0.920	-0.89	-3.93	0.63
2	48	2	50.0	34	-2.48	1.190	-2.60	-4.40	0.00
2	48	3	98.5	34	-1.54	1.424	-1.47	-4.37	1.02
2	48	4	197.3	34	-1.81	1.166	-1.93	-3.70	0.35
2	48	5	394.5	34	-0.97	0.803	-1.01	-2.41	1.14
2	98	2	50.0	34	-2.60	1.070	-2.40	-4.60	-0.40
2	98	3	98.5	34	-1.44	1.452	-1.37	-4.37	1.02
2	98	4	197.3	34	-2.03	0.971	-2.18	-4.21	-0.15
2	98	5	394.5	34	-1.00	0.777	-1.01	-2.66	0.38

Table 12.2. Precision Statistics

LEVEL	YSINUM	Random Effect	Mean	SigEst	CV
2	10	Between	49.56	0.604	1.22%
2	10	Within	49.56	0.111	0.22%
2	10	Total	49.56	0.614	1.24%
3	10	Between	98.55	1.027	1.04%
3	10	Within	98.55	0.147	0.15%
3	10	Total	98.55	1.037	1.05%
4	10	Between	195.95	1.333	0.68%
4	10	Within	195.95	0.324	0.17%
4	10	Total	195.95	1.372	0.70%
5	10	Between	392.63	3.533	0.90%
5	10	Within	392.63	0.725	0.18%
5	10	Total	392.63	3.607	0.92%
2	11	Between	49.27	0.806	1.64%
2	11	Within	49.27	0.165	0.33%
2	11	Total	49.27	0.823	1.67%
3	11	Between	98.00	1.401	1.43%
3	11	Within	98.00	0.223	0.23%
3	11	Total	98.00	1.419	1.45%
4	11	Between	195.21	2.044	1.05%
4	11	Within	195.21	0.397	0.20%
4	11	Total	195.21	2.083	1.07%
5	11	Between	390.71	3.573	0.91%
5	11	Within	390.71	0.874	0.22%
5	11	Total	390.71	3.678	0.94%

[figure not shown]
[figure not shown]
Figure 12.1. Scatterplot with Regression Line

Figure 12.2. Difference from Target Plot (for YSI Control Solution Tests)

Diff = control result - target

Table 12.3. Regression Statistics

Site	Term	Estimate	Std Error	d.f.e.	LCL	UCL	Adj. R ²	Sy.x
1	Intercept	-0.212	0.1029	302	-0.415	-0.010	0.9996	0.0120
1	Slope	0.995	0.0012	302	0.992	0.997	0.9996	0.0120
2	Intercept	-0.710	0.1057	270	-0.918	-0.502	0.9996	0.0117
2	Slope	0.989	0.0012	270	0.987	0.992	0.9996	0.0117

Section 13 – Meter Controls

Table 13.1. Meter Control Results Summary

Site	Lot	N	Mean	SD	Median	Min	Max	LL	UL
1	BLUE	20	126.6	2.19	126.0	123	132	110	138
1	GREEN	20	128.0	2.31	128.0	124	131	110	137
1	RED	20	129.0	1.79	129.0	125	131	109	136
2	BLUE	20	121.2	2.07	121.0	117	125	110	138
2	GREEN	20	123.2	1.79	122.5	121	127	110	137
2	RED	20	121.7	1.72	122.0	118	125	109	136

LL = Lower Limit

UL = Upper Limit
